#### **6.6.2.6 Management of Posterior Reversible Encephalopathy Syndrome/Reversible Encephalopathy Syndrome/Reversible Posterior Leukoencephalopathy Syndrome**

Posterior Reversible Encephalopathy Syndrome/Reversible Encephalopathy Syndrome/Reversible Posterior Leukoencephalopathy Syndrome (PRES/RPLS) is a neurological disorder that can present with headache, seizure, lethargy, confusion, altered mental function, blindness, and other visual or neurological disturbances. Mild to severe hypertension may be present. MRI is necessary to confirm the diagnosis of PRES/RPLS. Appropriate measures should be taken to control BP. In participants with signs or symptoms of PRES/RPLS, instructions in [Table 5](#) should be followed.

#### **6.6.2.7 Management of Hypocalcemia**

Serum calcium should be monitored per the SoA (Section 1.3). Corrected serum calcium should be used to assess the grade of hypocalcemia per CTCAE v4.0, using the following formula:

$$\text{Corrected calcium} = ([4 - \text{serum albumin in g/dL}] \times 0.8 + \text{serum calcium}).$$

The formula is not applicable when serum albumin concentration is normal ( $>4$  g/dL); in such situations, the total (uncorrected) serum calcium should be used instead.

Hypocalcemia should be treated per institutional guidelines (eg, using appropriate calcium, magnesium, and vitamin D supplementation) until resolution.

#### **6.6.2.8 Management of Hemorrhage**

Instructions in [Table 5](#) should be followed for the management of hemorrhage. Either resume at a reduced dose or discontinue lenvatinib/placebo depending on the severity and persistence of hemorrhage.

#### **6.6.2.9 Management of Gastrointestinal Perforation or Fistula**

Lenvatinib/placebo should be discontinued in any participants who develop gastrointestinal perforation of any grade or Grade 4 fistula.

See Appendix 7 for country-specific requirements.

#### **6.6.2.10 Management of QT Prolongation**

Lenvatinib/placebo should be withheld in the event of development of QT interval prolongation greater than 500 msec. Lenvatinib/placebo should be resumed at a reduced dose when QTc prolongation is resolved to  $<480$  msec or baseline. Monitor potassium, calcium and magnesium, and replenish as appropriate.

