#### Summary of changes in SoA:

- **Imaging:** while still on treatment per protocol (both pembrolizumab and lenvatinib) (not submitted to iCRO), then SOC
- **PE, Vital signs:** while still on treatment, then 30-day Safety FU, then SOC
- **ECG, MUGA:** while still on lenvatinib treatment then 30-day Safety FU, then SOC
- **Urinary laboratory tests, including 24-hour urine collection as specified per protocol:** while still on lenvatinib treatment, then 30-day Safety FU, then SOC
- **Hematology/Chemistry:** while still on treatment, then 30-day Safety FU, then SOC
- **T3, FT4, TSH:** while still on treatment, then 30-day Safety FU, then SOC
- **HIV, HBV, HCV:** while still on treatment, then 30-day Safety FU, then SOC
- **ECOG:** while still on treatment, then 30-day Safety FU, then SOC

See Appendix 7 for country-specific requirements.

The full SoA table below is retained for reference.

Study Period	Screening	Treatment Cycle = 21 days					EOT b	Posttreatment Visits			Notes
								Safety b,c	Efficacy Follow-Up Visits d	Survival	
Visit Timing/Cycle Number	-28 to -1	1	2	3 Onwards a		At D/C	30 Days and 90 Days After Last Dose	Q12W (± 7 d)	Q12W (± 7 d)		All procedures and assessments are to be performed prior to administration of study intervention unless otherwise indicated. Refer to Section 8.11 for visit details.
Cycle Day		1	8	15	1	15	1				
Scheduling Window (Days)	-28 to -1		±3	±3	±3	±3	±3	+7	±7	±7	
Administrative Procedures											
Informed Consent	X										Informed consent must be documented prior to any protocol-specific procedures are performed. Additional consent is required at disease progression.
Inclusion/Exclusion Criteria	X										
Participant Identification Card	X										
Medical/Surgical History	X										Significant medical/surgical history will be captured for last 10 years.
Demographics	X										
Staging	X										At initial diagnosis and at study entry.
BRAF status	X										At study entry.

Study Period	Screening	Treatment Cycle = 21 days					EOT b	Posttreatment Visits			Notes
								Safety b,c	Efficacy Follow-Up Visits d	Survival	
Visit Timing/Cycle Number	-28 to -1	1	2	3 Onwards a		At D/C	30 Days and 90 Days After Last Dose	Q12W (± 7 d)	Q12W (± 7 d)		All procedures and assessments are to be performed prior to administration of study intervention unless otherwise indicated. Refer to Section 8.11 for visit details.

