8. Has known history of human immunodeficiency virus (HIV) (HIV 1/2 antibodies). No testing of HIV is required unless mandated by local health authority. (See Appendix 7 for country-specific requirements.)
9. Has known history of or is positive for hepatitis B (hepatitis B surface antigen [HBsAg] reactive) or hepatitis C (HCV RNA [qualitative] is detected). No testing of hepatitis B or C is required unless mandated by local health authority. (See Appendix 7 for country-specific requirements.)
10. Has a history of (noninfectious) pneumonitis/interstitial lung disease that required steroids or has current pneumonitis/interstitial lung disease.
11. Has a history of active tuberculosis (*Bacillus tuberculosis*). (See Appendix 7 for country-specific requirements.)
12. Gastrointestinal malabsorption or any other condition that might affect the absorption of lenvatinib.
13. Has had a major surgery within 3 weeks prior to first dose of study intervention. Note: Adequate wound healing after major surgery must be assessed clinically, independent of time elapsed for eligibility.
14. Has preexisting Grade  $\geq 3$  gastrointestinal or nongastrointestinal fistula.
15. Has radiographic evidence of encasement or invasion of a major blood vessel, or of intratumoral cavitation.  
Note: The degree of proximity to major blood vessels should be considered because of the potential risk of severe hemorrhage associated with tumor shrinkage/necrosis following lenvatinib therapy.

16. Has active hemoptysis (bright red blood of at least 0.5 teaspoon) within 3 weeks prior to the first dose of study intervention.
17. Has clinically significant cardiovascular disease within 12 months from first dose of study intervention, including New York Heart Association Class III or IV congestive heart failure, unstable angina, myocardial infarction, cerebral vascular accident, or cardiac arrhythmia associated with hemodynamic instability.  
Note: Medically controlled arrhythmia would be permitted.
18. Has urine protein  $\geq 1$  g/24-hour.  
Note: Participants with  $\geq 2+$  ( $\geq 100$  mg/dL) proteinuria on urine dipstick testing (or urinalysis) will undergo 24-hour urine collection for quantitative assessment of proteinuria.
19. Prolongation of QTcF interval to  $>480$  ms.  
Note: If the QTcF is prolonged to  $>480$  ms in the presence of a pacemaker, contact the Sponsor to determine eligibility. (See Appendix 7 for Country-specific requirements.)

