### 6.6.2 Dose Modification With Lenvatinib/Placebo

Lenvatinib/placebo dose reduction and interruption for participants who experience lenvatinib/placebo-pembrolizumab combination therapy-related toxicity will be in accordance with the dose modification guidelines described in [Table 5](#). An interruption of study intervention for more than 28 days will require Sponsor consultation and approval before treatment can be resumed. Participants who discontinue lenvatinib/placebo due to untoward toxicities can continue on the study receiving pembrolizumab as monotherapy.

The starting dose of lenvatinib/placebo is 20 mg/day. Dose reductions of lenvatinib/placebo occur in succession based on the previous dose level (14, 10, and 8 mg/day). Any dose reduction below 8 mg/day must be discussed with the Sponsor. Once the study intervention

dose has been reduced, it may not be increased at a later date, unless the dose has been mistakenly decreased; in this situation, Sponsor's approval is required to increase the dose.

Refer to the subsections below for management of hypertension (Section 6.6.2.1), proteinuria (Section 6.6.2.2), diarrhea (Section 6.6.2.3), hepatotoxicity (Section 6.6.2.4), thromboembolic events (Section 6.6.2.5), posterior reversible encephalopathy syndrome/reversible encephalopathy syndrome/reversible posterior leukoencephalopathy syndrome (Section 6.6.2.6), hypocalcemia (Section 6.6.2.7), hemorrhage (Section 6.6.2.8), gastrointestinal perforation or fistula formation (Section 6.6.2.9), QT prolongation (6.6.2.10), and osteonecrosis of the jaw (Section 6.6.2.11) as appropriate, before consulting the dose modification table ([Table 5](#)). For overlapping toxicities of pembrolizumab and lenvatinib/placebo, please refer to Section 6.6.3.

Table 5 Dose Modification Guidelines for Lenvatinib/Placebo-related Adverse Events

Treatment-related Toxicity a,b	Management	Dose Adjustment
Grade 1 or Tolerable Grade 2		
	Continue treatment	No change
Intolerable Grade 2c,d or Grade 3e,f		
First occurrence	Interrupt lenvatinib/placebo until resolved to Grade 0-1, or tolerable Grade 2	Reduce lenvatinib/placebo dose to 14 mg once a day (1-level reduction)
Second occurrence (same toxicity or new toxicity)	Interrupt lenvatinib/placebo until resolved to Grade 0-1, or tolerable Grade 2	Reduce lenvatinib/placebo dose to 10 mg once a day (1-level reduction)

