### **8.3.3 Electrocardiograms**

Electrocardiograms will be obtained as designated in the SoA (Section 1.3). Complete, standardized, 12-lead ECG recordings that permit all 12 leads to be displayed on a single page with an accompanying lead II rhythm strip below the customary  $3 \times 4$  lead format are to be used. In addition to a rhythm strip, a minimum of 3 full complexes should be recorded from each lead simultaneously. Participants must be in the recumbent position for a period of 5 minutes prior to the ECG. The Fridericia correction method for calculating QTc will be used.

An ECG abnormality may meet the criteria of an AE as described in this protocol (see Appendix 3) and the CRF Completion Guidelines. In these instances, the AE corresponding to the ECG abnormality will be recorded on the appropriate CRF.

QTc prolongation has been seen in some lenvatinib studies. Monitor electrocardiograms every cycle (as specified in the Schedule of Assessments) in patients with congenital long QT syndrome, congestive heart failure, bradyarrhythmias, or those who are taking drugs known to prolong the QT interval, including Class Ia and III antiarrhythmics. Refer to the lenvatinib IB.

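### The lenvatinib withhold rule in Section 6.6.2.10 is set on an uncorrected QT interval, whereas the resume rule and the entry criterion use corrected QT

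*Combined protocol and SAP*

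**What the plan says.** Section 6.6.2.10 has two consecutive dosing sentences. The first reads "Lenvatinib/placebo should be withheld in the event of development of QT interval prolongation greater than 500 msec". The second reads "Lenvatinib/placebo should be resumed at a reduced dose when QTc prolongation is resolved to" below 480 msec or baseline. The first names no correction; the second is on QTc.

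The other places that bear on the metric are:

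- Section 8.3.3: "The Fridericia correction method for calculating QTc will be used". The same section records that "QTc prolongation has been seen in some lenvatinib studies".
- Section 5.2, exclusion 19: "Prolongation of QTcF interval to" above 480 ms. The UK version in Section 10.7.4 also specifies Fridericia's formula, with the same limit.
- Section 6.6.2: investigators go to the toxicity-specific subsections, including 6.6.2.10, "as appropriate, before consulting the dose modification table" (Table 5). Once the "dose has been reduced, it may not be increased at a later date", unless the decrease was a mistake and the Sponsor approves.
- Section 1.3, summary of changes: ECGs continue "while still on lenvatinib treatment then 30-day Safety FU, then SOC".

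**The concern.** One dosing rule uses two metrics: it stops the drug on QT and restarts it on QTc. The two coincide only at a heart rate of 60/min. A site that follows the withhold sentence as written can go wrong in either direction. At faster rates it can leave a participant on full dose with a QTcF above 500 msec. At slow rates it can stop the drug on a tracing that already satisfies the restart limit.

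This is the only QT-specific dosing rule in the protocol, for a drug that the protocol itself links to QTc prolongation. After Cycle 2, routine ECGs come only every fourth cycle (12 weeks) unless the participant is high-risk or more are clinically indicated, so a missed trigger may not be rechecked soon. Participants with bradyarrhythmias, who are most open to the opposite error, have an ECG every cycle. An unnecessary withhold errs on the cautious side, but it has a lasting cost, because restart is at a lower dose and re-escalation is largely barred.

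**Working it through.** **Inputs.** Withhold limit 500 msec on QT, and resume limit 480 msec on QTc (Section 6.6.2.10). Correction: Fridericia (Section 8.3.3). The documents give no heart rates, so those below are assumed for illustration. There is no figure in the plan to reproduce.

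**Formula.** QTcF = QT ÷ RR^(1/3) with RR = 60/HR, that is QTcF = QT × (HR/60)^(1/3). The raw QT at which QTcF equals 500 msec is 500 × (60/HR)^(1/3).

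| Heart rate (/min) | QTcF when raw QT = 500 msec | Raw QT at which QTcF = 500 msec |
|---|---|---|
| 50 | 470.5 | 531.3 |
| 55 | 485.7 | 514.7 |
| 60 | 500.0 | 500.0 |
| 70 | 526.4 | 475.0 |
| 80 | 550.3 | 454.3 |
| 100 | 592.8 | 421.7 |

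The literal rule fixes the trigger at a raw QT of 500 msec in every row. A QTcF rule would move it as in the last column.

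**Missed triggers, above 60/min.** These are ECGs with QTcF above 500 msec but raw QT of 500 msec or less:

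- 70/min: raw QT 476–500, QTcF 501–526
- 80/min: raw QT 455–500, QTcF 501–550
- 100/min: raw QT 422–500, QTcF 500–593. For example, 430 × (100/60)^(1/3) = 509.8

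At a raw QT of 500 msec, QTcF exceeds the limit by 26 msec at 70/min, 50 at 80/min and 93 at 100/min.

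**Unnecessary withholds, at slow rates.** A raw QT of 500 msec gives a QTcF of 480 msec at HR = 60 × (480/500)³ = 53.1/min. Below that rate, a raw QT just over 500 msec calls for a withhold while QTcF is already under the resume limit. At 50/min this covers raw QT 501–510, with QTcF 471.5–479.9. For example, 505 × (50/60)^(1/3) = 475.2. Between about 53 and 60/min the literal rule can still withhold with QTcF below 500 msec, but the resume limit is not yet met at that point.

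**The case against.** The strongest reply is that the section resolves itself. The resume sentence refers back to the prolongation that caused the withhold and calls it QTc, and Section 8.3.3 fixes the formula. A reading under which one ECG can both stop and restart the drug is, on its face, not what was meant. Section 8.3.3 also uses QT loosely, when it speaks of drugs that prolong the QT interval. A miss would need an investigator to set aside a corrected value that the protocol already requires. ECGs are recorded after five minutes recumbent, so 100/min should not be taken as typical. Table 5 and investigator judgment remain as backstops. Placebo is discontinued, lenvatinib continues only by exception after consulting the Sponsor, and Section 6 carries a note that its original text is kept for reference.

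Most of this stands as a limit on impact. QTcF was probably the intent, and a missed case is not necessarily unmanaged. It does not remove the defect. Every other numeric QT limit in the protocol is expressly corrected, so the one unqualified limit can be read as deliberate. Section 6.6.2.7, three subsections earlier, takes care to separate corrected from uncorrected calcium. The reference note does not switch the rule off for participants still taking lenvatinib, whose ECGs continue.

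**Conclusion.** The concern holds. The withhold sentence names no correction, the related limits are corrected, and no statement in the protocol equates the two. Followed as written, the rule can give the wrong action in both directions, by 26 to 93 msec of QTcF at 70 to 100/min when raw QT is 500 msec. Below about 53/min it can contradict its own resume limit.

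These sizes rest on assumed heart rates and on a literal reading. How many participants are affected cannot be estimated from the documents, and after Amendment 07 the number still exposed should be small. This is an inconsistency in a safety rule, probably a drafting slip. It touches no endpoint, analysis or error rate. Because it concerns a stop-dose threshold that is still in force for exception participants, it should be corrected.

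**What to change.** In Section 6.6.2.10, state the withhold limit as QTcF prolongation greater than 500 msec. For consistency, state the resume limit as QTcF below 480 msec or baseline; this second edit is stylistic, since Section 8.3.3 already makes QTc Fridericia-corrected. Both thresholds stay as they are.

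The cost is a wording change in two sentences, made by a clarification letter to sites or at the next amendment. No added ECGs, measurements or analyses are needed.

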#### **6.6.2.11 Management of Osteonecrosis of the Jaw**

Perform an oral examination prior to treatment with lenvatinib/placebo and periodically during lenvatinib/placebo treatment. Advise participants regarding good oral hygiene practices. Avoid invasive dental procedures, if possible, while on lenvatinib/placebo treatment, particularly in participants at higher risk. For participants requiring invasive dental procedures, discontinuation of bisphosphonate treatment may reduce the risk of ONJ. Withhold lenvatinib/placebo if ONJ develops and restart based on clinical judgment of adequate resolution (see Section 6.6.4).

### **6.6.3 Dose Modifications for Overlapping Toxicities**

Participants who experience an unacceptable toxicity that is attributed to lenvatinib/placebo in the opinion of the investigator and the Sponsor, may permanently discontinue lenvatinib/placebo, but may continue with pembrolizumab, upon resolution of toxicity to Grade 0 or 1 or baseline, until unacceptable toxicity or progression. Participants who discontinue pembrolizumab due to untoward toxicities cannot continue on the study receiving only lenvatinib/placebo.

Based on the known toxicity profiles of pembrolizumab and lenvatinib, certain treatment-related AEs are uniquely associated with one drug versus the other. For example, hypertension, arterial thrombotic events, proteinuria, and hemorrhagic events are known risks

for lenvatinib treatment, while immune-related AEs are risks for pembrolizumab treatment. However, certain AEs, such as diarrhea, hypothyroidism, and liver enzyme elevation, may be initially considered attributable to either study intervention. Therefore, evaluation of attribution is important for determining the study intervention most likely related to the AE, or an alternative etiology, and subsequently proper clinical management. The following aspects should be considered:

1. Timing of AE onset

Since lenvatinib/placebo is dosed daily and continuously due to a relatively short half-life (~28 hours), and pembrolizumab is dosed Q3W due to a long half-life, lenvatinib/placebo can be interrupted to assess whether an AE improves/resolves with dechallenge (ie, interruption of treatment) based on the following 2 scenarios:

- If an AE is identified during a treatment cycle (ie, between 2 pembrolizumab doses), only lenvatinib/placebo dose interruption is needed.
- If an AE is identified at the beginning of a treatment cycle, lenvatinib/placebo can be interrupted and dosing of pembrolizumab should be held.

If the participant recovers from an AE in response to lenvatinib/placebo interruption (ie, positive dechallenge), the event is more likely to be related to lenvatinib/placebo. Otherwise, after excluding other alternative explanations, an immune-related AE should be considered.

2. Severity of AE

If an AE is suspected to be treatment related and is severe/life-threatening at the time of onset or is rapidly worsened, action including interrupting both drugs and initiating treatment with a corticosteroid (with exception of hypothyroidism, TIDM) and other supportive care should be taken promptly.

3. Participants receiving the combination therapy (pembrolizumab + lenvatinib/placebo) must discontinue study intervention if any of the following occur:

- ALT or AST  $>5 \times$  ULN for more than 2 weeks  
Pembrolizumab will have already been permanently discontinued per [Table 3](#), but lenvatinib/placebo may be administered at a reduced dose by the time this criterion is met and must be permanently discontinued immediately.
- ALT or AST  $>3 \times$  ULN and (TBL  $>2 \times$  ULN or INR  $>1.5$ )  
Although [Table 3](#) advises pembrolizumab to be withheld (interrupted), and [Table 5](#) advises lenvatinib/placebo to have no dose modification or a reduction, if this criterion is met, both drugs must be permanently discontinued immediately.

#### **6.6.4 Other Allowed Dose Interruptions for Lenvatinib/Placebo and Pembrolizumab**

If the participant is receiving treatment with lenvatinib/placebo and requires surgery during the study, the stop time and restart time of lenvatinib/placebo should be as follows:

- For minor procedures: stop lenvatinib/placebo at least 2 days before the procedure and restart it at least 2 days after, once there is evidence of adequate healing and no risk of bleeding.
- For major procedures: stop lenvatinib/placebo at least 1 week (5 half-lives) prior to surgery and then restart it at least 2 weeks after, once there is evidence of adequate healing and no risk of bleeding.
- For scheduled dental surgery or invasive dental procedures, stop lenvatinib for at least 1 week before the procedure, then restart lenvatinib when deemed clinically appropriate.

Pembrolizumab may be interrupted for situations other than treatment-related AEs such as medical/surgical events or logistical reasons not related to study therapy. Participants should be placed back on study therapy within 3 weeks of the scheduled interruption, unless otherwise discussed with the Sponsor. The reason for interruption should be documented in the participant's study record.

#### **6.7 Intervention After the End of the Study**

Upon study completion, participants are to be discontinued and may be enrolled in an extension study using pembrolizumab or lenvatinib monotherapy, if available.

#### **6.8 Clinical Supplies Disclosure**

The emergency unblinding call center will use the intervention/randomization schedule for the study to unblind participants and to unmask study intervention identity. The emergency unblinding call center should only be used in cases of emergency (see Section 8.1.11). If the emergency unblinding call center is not available for a given site in this study, the central electronic intervention allocation/randomization system (IRT) should be used to unblind participants and to unmask study intervention identity. The Sponsor will not provide random code/disclosure envelopes or lists with the clinical supplies.

See Section 8.1.11 for a description of the method of unblinding a participant during the study, should such action be warranted.

## 6.9 Standard Policies

At the close of the study after unblinding, a letter is to be sent by the investigator to those participants who received placebos in the image of the competitor's product to provide the following advice:

“You have participated in a study conducted by the Sponsor. This letter is to advise you that you were among those who received a look-alike capsule created to resemble the drug LENVIMA® (lenvatinib) as much as possible. You did not receive the active drug LENVIMA (lenvatinib) as manufactured by Eisai.”

